7. Adequate organ function per screening labs

|                                    |  |
|------------------------------------|--|
|                                    | 8. Cannot have QT interval corrected for heart rate using Fridericia's formula ( $QTcF$ ) $\geq 470$ ms calculated. Any clinically significant abnormalities detected require triplicate ECG results and a mean $QTcF < 470$ ms calculated from 3 ECGs obtained over a brief period (eg, 30 minutes)   |
| STATISTICAL CONSIDERATIONS  | A Simon's 2-stage design will be applied. The null hypothesis that the true response rate is 2% will be tested against a one-sided alternative. In the first stage, 18 subjects will be accrued. If there are 0 responses in these 18 subjects, enrollment will be stopped. Otherwise, 10 additional subjects will be accrued for a total of 28. The null hypothesis will be rejected if 3 or more responses (complete/partial) are observed in 28 subjects and further investigation will be warranted. This design yields a type I error rate of 0.02 and power of 80% when the true response rate is 15% or larger. |
| TOTAL NUMBER OF SUBJECTS    | N = Approximately 28   |
| ESTIMATED ENROLLMENT PERIOD | Estimated 12 months  |
| ESTIMATED STUDY DURATION    | Estimated 24 months  |

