## 12.7 Interim Analysis/Criteria for Stopping Study

Though there has been limited experience with single agent CTLA-4 blockade in metastatic urothelial cancer, prior studies exploring combination PD-1/PD-L1 plus CTLA-4 blockade in metastatic urothelial cancer have reported a treatment-related Grade  $\geq 3$  adverse event rate of approximately 30%. A stopping rule for excessive toxicity will be employed after 6, 12, 18, and 24 subjects finish at least one cycle of treatment. This safety stopping rule will be performed with respect to all treatment-related Grade  $\geq 3$  adverse events. Two-sided 95% exact binomial confidence intervals (CIs) of these treatment-related Grade  $\geq 3$  adverse event rates will be constructed. If their lower bounds exceed 33%, the study drug will be considered unacceptably toxic for this patient population and enrollment will be halted. This corresponds to  $\geq 5$  out of 6 patients with grade  $\geq 3$  adverse events,  $\geq 8$  out of 12 patients with grade  $\geq 3$  adverse events,  $\geq 10$  out of 18 patients with grade  $\geq 3$  adverse events, and  $\geq 13$  out of 24 subjects with grade  $\geq 3$  adverse events.

There is a possibility of stopping at the 1st stage if no patients respond to treatment. In addition, the study accrual may be suspended in the case when none of the first 17 patients respond and

the decision to move onto the 2nd stage hinges on the response of the 18th patient. Otherwise, during these safety analyses, enrollment will continue.

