### 13.2 Tisch Cancer Institute Cancer Center Data Safety Monitoring Committee

**HCRN will provide the following for the DSMC to review:**

- Adverse event summary report
- Audit results, if applicable
- Data related to stopping/decision rules described in study design
- Study accrual patterns
- Protocol deviations

The DSMC will review study data at least every 6 months. Documentation of DSMC reviews will be provided to sponsor-investigator and HCRN. Issues of immediate concern by the DSMC will be brought to the attention of the sponsor-investigator and other regulatory bodies as appropriate. The sponsor-investigator will work with HCRN to address the DSMC's concerns.

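### Section 12.7's only toxicity stopping rule counts a drug-related death the same as a Grade 3 event, and no written trigger pauses enrolment after such a death

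*Combined protocol and SAP*

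**What the plan says.** Section 12.7 sets the timing: "A stopping rule for excessive toxicity will be employed after 6, 12, 18, and 24 subjects finish at least one cycle of treatment". The event counted is pooled: "This safety stopping rule will be performed with respect to all treatment-related Grade" 3 or higher adverse events. The criterion uses exact two-sided 95% binomial intervals: "If their lower bounds exceed 33%, the study drug will be considered unacceptably toxic for this patient population and enrollment will be halted". The section translates this into at least 5 of 6, 8 of 12, 10 of 18 and 13 of 24 patients. After allowing accrual to be suspended while the 18th patient's response is awaited, it adds: "Otherwise, during these safety analyses, enrollment will continue".

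Deaths are handled elsewhere as follows:

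- Sections 11.1.2, 11.2.2 and 11.6.5 cover classification and expedited reporting.
- Section 11.3 has the sponsor-investigator review each serious event for expectedness and relatedness.
- Section 11.4 covers the 7- and 15-day FDA reports.
- Section 13.1 places the study under the guidance of an institutional data and safety monitoring plan (DSMP).
- Section 13.2 lists stopping-rule data among the items the committee receives and lets it escalate matters of immediate concern. On frequency it says: "The DSMC will review study data at least every 6 months".

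None of these sections says that enrolment pauses, or that the committee meets, because a treatment-related death has occurred.

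**The concern.** A rule built on one pooled count responds to how many patients have a Grade 3 or higher event, not to how severe the events are. Its reference point is a rate of about 30% for Grade 3 or higher events, and a halt requires more than half of the patients to be affected at every look. A few drug-related deaths, which most monitoring committees would want to examine before the next patient is enrolled, leave such a rule far from its limit.

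The protocol itself makes fatal toxicity foreseeable. Section 10.1.4 lists intestinal perforation, pneumonitis, encephalitis and Guillain-Barré among the risks. Appendix 1 singles out events with a high likelihood of morbidity or mortality. Section 12.7 acknowledges limited experience with single-agent CTLA-4 blockade in this disease. A pause is written in for the futility decision at the 18th patient, but none for a drug-related death.

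**Working it through.** **Inputs.** From 12.7: looks at 6, 12, 18 and 24 subjects; exact two-sided 95% interval; threshold 33%; printed limits 5, 8, 10 and 13; benchmark about 30%. From 12.3: up to 28 subjects. Assumed for illustration: true treatment-related death rates of 1%, 2% and 10%. A fatal event is taken as Grade 5 on CTCAE v4.03, the scale the protocol adopts; the protocol does not print that definition.

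**1. The plan's own limits.** The exact lower bound for x events in n patients is the 2.5% quantile of a Beta(x, n − x + 1) distribution.

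| Look | Highest printed count with no halt | Lower bound | Printed limit | Lower bound | First count above 33% |
|---|---|---|---|---|---|
| 6 | 4 | 22.3% | 5 | 35.9% | 5 |
| 12 | 7 | 27.7% | 8 | 34.9% | 8 |
| 18 | 9 | 26.0% | 10 | 30.8% | 11 (35.7%) |
| 24 | 12 | 29.1% | 13 | 32.8% | 14 (36.6%) |

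The first two limits reproduce. The last two do not: under the stated criterion they would be 11/18 and 14/24. Under the printed counts, 4/6, 7/12, 9/18 or 12/24 does not require a halt, whatever the grades. Under the stated criterion, 10/18 and 13/24 would not either.

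**2. Response to deaths alone at a true rate of 10%.** Let f_k(x) be the probability of reaching look k without an earlier halt and with x events in total. Then f_k(x) = Σ f_(k−1)(y) · b(x − y; 6, p), summed over y below the previous limit, where b is the binomial probability. The chance of halting at look k is the sum of f_k(x) over x at or above the limit.

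- Look 1: 6 × 0.1⁵ × 0.9 + 0.1⁶ = 0.000054 + 0.000001 = 0.000055.
- Cumulative over the four looks: 0.0000550, 0.0000574, 0.0000589, 0.0000590, or about 0.006%.
- At least one death in 28: 1 − 0.9²⁸ = 1 − 0.0523 = 0.948, or 95%.
- At least two deaths in 28: 1 − 0.0523 − 28 × 0.1 × 0.9²⁷ = 1 − 0.0523 − 0.1628 = 0.785, or 78%.

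**3. Response when non-fatal events are added.** Suppose 10% of patients have a fatal event and a different 30% have a non-fatal Grade 3 or higher event. Then 40% are affected, and the same recursion at p = 0.40 gives cumulative halting probabilities of 4.1%, 7.8%, 15.9% and 18.7%. At p = 0.30, with no added deaths, the rule halts 3.5% of trials.

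**4. How often a Grade 5 pause would occur.** The chance of at least one event in 28 is 1 − 0.99²⁸ = 0.245 (25%) at a 1% death rate, and 1 − 0.98²⁸ = 0.432 (43%) at 2%.

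**5. Does a cycle 1 death count?** Looks are taken after subjects finish at least one cycle. The text does not say whether a patient who dies during cycle 1 counts towards the 6, 12, 18 or 24.

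**The case against.** The strongest reply is that a numerical rule is not the only safeguard. Section 12.7 does not mandate a halt after four deaths in six patients, but it does not forbid one. Deaths not clearly due to progression are reported within 24 hours, the sponsor-investigator reviews serious events promptly, FDA reports follow, and the committee can raise urgent issues. The monitoring plan cited in 13.1 may already require review of a drug-related death. The four-in-six case is also remote: at a 10% death rate the chance of four or more deaths in six is 0.13%. All of this stands. It limits the point to the absence of a written obligation in this protocol.

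Three stronger readings are tempting, and the documents do not support them.

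- **That the rule has a 0.006% chance of halting a trial with 10% fatal toxicity.** That figure counts deaths alone. With non-fatal events in the count the chance is higher: 18.7% in the example above.
- **That most looks reach the committee after enrolment has ended.** With 28 subjects over the planned enrolment period ("Estimated 12 months") and one 28-day cycle (0.92 months), look 2 falls at 12 ÷ (28/12) + 0.92 = 6.06 months, just after a meeting assumed at month 6. Other even-accrual conventions put it before that meeting: first subject at month 0 gives 11 ÷ (28/12) + 0.92 = 5.63; 27 equal gaps give 11 × 12/27 + 0.92 = 5.81; mid-interval entry gives 11.5 ÷ (28/12) + 0.92 = 5.85. The meeting dates are themselves assumed, six months is the longest permitted interval, and no text makes the rule wait for a meeting.
- **That the 30% benchmark consists mainly of non-fatal events.** Section 12.7 gives no split by grade.

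**Conclusion.** The point holds. The only toxicity stopping rule gives a drug-related death no more weight than a Grade 3 event, and up to 4/6, 7/12, 9/18 or 12/24 affected patients require no halt even if all the events are fatal. The protocol supplies reporting and discretionary escalation, but no pause or review trigger for such a death. At a 10% death rate the rule responds to deaths alone in about 0.006% of trials, while 95% would see at least one drug-related death and 78% at least two among 28.

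These figures assume independent patients with a constant risk, all 28 enrolled, and the printed limits followed as written. The 18.7% further assumes that fatal and non-fatal events fall in different patients. The conclusion on written triggers is conditional on the unseen monitoring plan. The six-monthly minimum in 13.2 does not guarantee that the committee sees each look when it is reached, and the timing point goes no further than that.

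**What to change.** 1. **Section 12.7, new trigger.** State that any Grade 5 event judged treatment-related suspends new enrolment until an ad hoc DSMC review is documented. Name which of the five relatedness categories in 11.1.5 count. If the institutional plan already requires this, cross-reference it instead. The trigger should apply whether or not the subject finished cycle 1.
2. **Section 12.7, existing rule.** Keep a Grade 3 or higher rule, but reconcile the printed 10/18 and 13/24 with the stated two-sided exact 33% criterion, which gives 11/18 and 14/24.
3. **Section 13.2.** State that the data for each 12.7 look go to the DSMC when the look is reached.

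The cost is a short amendment and a few ad hoc reviews by the existing committee. The downside is a possible brief accrual pause: at least one in 25% of trials if the true drug-related death rate is 1%, and in 43% if it is 2%. Dosing and the management of patients already on treatment are unaffected.

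### The toxicity stopping counts at 18 and 24 patients do not follow from the stated 33% rule: 10/18 and 13/24 have exact lower bounds of 30.8% and 32.8%

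*Combined protocol and SAP*

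**What the plan says.** Section 12.7 (Interim Analysis/Criteria for Stopping Study) schedules the looks: "A stopping rule for excessive toxicity will be employed after 6, 12, 18, and 24 subjects finish at least one cycle of treatment". The event is defined next: "This safety stopping rule will be performed with respect to all treatment-related Grade" ≥3 adverse events. The statistic is given as "Two-sided 95% exact binomial confidence intervals (CIs) of these treatment-related Grade" ≥3 event rates, and the decision is: "If their lower bounds exceed 33%, the study drug will be considered unacceptably toxic for this patient population and enrollment will be halted".

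The section then states that this corresponds to at least 5 of 6, at least 8 of 12, at least 10 "out of 18 patients with grade" ≥3 events, and at least 13 "out of 24 subjects with grade" ≥3 events. The same paragraph says that earlier combination studies "have reported a treatment-related Grade" ≥3 adverse event rate of approximately 30%.

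The exact method is not named, and no order of precedence is given between the interval sentence and the list of counts.

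**The concern.** The counts are presented as a translation of the interval rule, so each should be the smallest number of events whose lower bound is above 33%. At 18 and 24 patients they are not, and the plan therefore holds two rules that disagree at exactly 10/18 and exactly 13/24.

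This is the only numeric toxicity boundary for halting enrolment in the document. Section 13.2 sends the monitoring committee the data for the stopping and decision rules, so the committee would have to choose between the two forms with an unfavourable result already in view. The look at 18 patients also coincides with the end of stage 1 in Section 12.3.

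**Working it through.** **Inputs (all from Section 12.7).** Looks at n = 6, 12, 18 and 24; two-sided 95% exact binomial interval, so 2.5% in the lower tail; cut-off 33%; printed counts 5, 8, 10 and 13.

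**Formula.** The Clopper-Pearson lower bound L for x events in n patients solves P(X ≥ x | n, L) = 0.025. Equivalently, L is the 0.025 quantile of a Beta(x, n − x + 1) distribution. So L > 33% exactly when P(X ≥ x | n, 0.33) < 0.025.

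**Step 1: reproduce the plan's counts.** As a hand check at 5/6: 6 × 0.33⁵ × 0.67 + 0.33⁶ = 0.0157 + 0.0013 = 0.0170, which is below 0.025, so 5/6 meets the rule.

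| n | Printed count | L at printed count | P(X ≥ x) at 0.33 | L at one fewer event | L above 33%? |
|---|---|---|---|---|---|
| 6 | 5 | 35.9% | 0.0170 | 22.3% | yes |
| 12 | 8 | 34.9% | 0.0176 | 27.7% | yes |
| 18 | 10 | 30.8% | 0.0405 | 26.0% | no |
| 24 | 13 | 32.8% | 0.0262 | 29.1% | no |

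The counts at 6 and 12 reproduce. Those at 18 and 24 do not.

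**Step 2: counts that meet the stated rule.** One more event gives L = 35.7% at 11/18 (tail 0.0133) and 36.6% at 14/24 (tail 0.0094). The stated rule therefore gives 5, 8, 11 and 14. Reading 33% as one third gives the same four counts.

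**Step 3: readings that give the printed counts.**

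- Two-sided 95% Clopper-Pearson with a 30% cut-off: all four printed counts pass and each next lower count fails (see the table in Step 1).
- One-sided 95% Clopper-Pearson with the 33% cut-off: L = 41.8%, 39.1%, 34.1% and 35.8% at the printed counts, and 27.1%, 31.5%, 29.1% and 31.9% at one fewer.
- Two-sided 95% Sterne interval (inverted two-sided exact test) with 33%: L = 41.1%, 37.0%, 33.03% and 33.9%.

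The first contradicts the printed 33%, the second contradicts the word two-sided, and the third is a less common method that the plan does not name.

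**Step 4: effect on the chance of stopping.** Start with no events. At each look add a Binomial(6, p) number of new events, record the probability of reaching the boundary, and carry forward only the paths below it. The sum over the four looks is the overall stopping probability.

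| True rate p | Printed counts (5, 8, 10, 13) | Implied by 33% (5, 8, 11, 14) |
|---|---|---|
| 30% | 3.5% | 2.1% |
| 33% | 6.2% | 3.8% |
| 40% | 18.7% | 11.8% |
| 50% | 51.3% | 37.6% |
| 60% | 83.6% | 72.6% |

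Most of the difference arises at the 18-patient look. At p = 50% the probability of stopping there is 20.9% with the printed count and 8.5% with the implied count; at the 24-patient look it is 7.6% and 6.3%.

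**The case against.** Several points can be made for the plan.

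- **Method.** The text says exact without naming Clopper-Pearson, and the Sterne interval reproduces all four counts at 33%. This is a true caveat, but a thin one: 10/18 passes by 0.03 percentage points and fails if 33% means one third. Blaker's exact interval (32.6%) and the mid-P interval (32.7%) also fall short at 10/18, though both clear 33% at 13/24. An unqualified exact binomial interval is ordinarily Clopper-Pearson.
- **Origin of the counts.** It is tempting to conclude that the counts were built on the 30% benchmark. The one-sided 95% reading explains them equally well, with 33% and every count left intact. The documents cannot separate the two, so the origin remains open.
- **Size.** The two misses are unequal: 10/18 falls short by 2.2 points, whereas 13/24 falls short by 0.2 points and rounds to 33%. At true rates of 30% and 33% the overall gap is only 1.3 and 2.4 points; gaps of 11 to 14 points need a true rate of 50% to 60%.
- **Direction and reach.** The printed counts stop earlier, so following them errs towards halting. The look at 24 may never take place if stage 1 ends with no responses. If it does, at most 28 − 24 = 4 planned patients remain.

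These points limit the consequences and leave the cause uncertain. They do not remove the contradiction: every reading that rescues the counts needs a change to the text, or a method that the text does not state.

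**Conclusion.** The concern holds. Under the two-sided 95% Clopper-Pearson interval, two of the four printed stopping counts are one patient lower than the 33% rule they are said to represent: 10/18 instead of 11/18, and 13/24 instead of 14/24. The mismatch at 18 is clear, and the one at 24 is marginal. The practical result is an undefined decision at one exact count at each of those looks. Between the two forms, the overall stopping probability differs by 1.3 points at a true rate of 30%, about 7 at 40% and 13.7 at 50%.

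The bounds rest on Clopper-Pearson being the intended exact method. The stopping probabilities also assume independent patients with a common event rate, one yes/no outcome per patient fixed when that patient is counted, and all four looks taking place with no stop for lack of response.

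It needs correction before use because it is a safety boundary that, as written, gives two answers.

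**What to change.** Rewrite the rule in Section 12.7 so that the sentence and the counts agree. Three versions are internally consistent under Clopper-Pearson:

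1. two-sided 95%, cut-off 33%, counts 5/6, 8/12, 11/18 and 14/24;
2. two-sided 95%, cut-off 30%, counts as printed;
3. one-sided 95%, cut-off 33%, counts as printed.

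Which toxicity rate and which level of certainty should halt enrolment is for the sponsor to decide; this review does not choose among them. Whichever is adopted, name the interval method, state its sidedness, say that the counts govern (or that the interval does), and give the overall stopping probability at a few true rates, as in the table above. In the same edit, repeat the treatment-related qualifier in the list of counts, which at present refers only to grade ≥3 adverse events.

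The cost is a short protocol correction, with no extra patients, visits or procedures.

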### **5.1.3 Re-treatment of Subjects Progressing within 1 Year of Completing Initial Tremelimumab**

Patients that complete the initial 7 cycles of tremelimumab then have evidence of disease progression per RECIST 1.1 (with or without confirmation) during the 1-year follow-up period may be eligible for re-treatment with up to 7 additional cycles of tremelimumab. Such patients are required to meet the eligibility criteria outlined in Section 3.3. Testing done during progression may be used for screening prior to re-treatment. Subjects should follow the same schedule of events/procedures for the initial Cycles 1-7 of tremelimumab.

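### Crossing the toxicity boundary has no stated effect beyond halting enrollment, and the last look is at 24 of 28 subjects, when little enrollment is left to halt

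*Combined protocol and SAP*

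**What the plan says.** Section 12.7 of the combined protocol and SAP places the toxicity looks "after 6, 12, 18, and 24 subjects finish at least one cycle of treatment". On scope it says: "This safety stopping rule will be performed with respect to all treatment-related Grade" ≥3 adverse events, with no restriction to a cycle. The criterion is a two-sided 95% exact binomial interval whose lower bound exceeds 33%. On crossing, "the study drug will be considered unacceptably toxic for this patient population and enrollment will be halted". The section prints counts said to correspond: at least 5/6, 8/12, 10/18 and 13/24. It also says that, apart from a possible suspension around the 18th subject for efficacy, enrollment continues while the safety analyses are done.

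Initial treatment is up to 7 cycles of 28 days (Section 5.1). Under Section 5.1.3, subjects who complete it and progress during the one-year follow-up "may be eligible for re-treatment with up to 7 additional cycles of tremelimumab". Sections 3.3 (re-treatment criteria), 5.1.3 and 6.4 (discontinuation of therapy) do not mention the Section 12.7 rule.

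Under Section 13.2 the DSMC receives data on the stopping rules: "The DSMC will review study data at least every 6 months". The final toxicity analysis (Section 12.6.2) is a frequency table of all dosed subjects.

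**The concern.** A finding that the drug is too toxic for this population bears first on the people already receiving it. The rule as written attaches that finding only to people not yet enrolled. Its last application comes when nearly everyone is enrolled, many subjects are still in their initial course, and most re-treatment has yet to begin. If the boundary is crossed, investigators and the DSMC have no text saying what it means for subjects on drug or for a re-treatment about to start. If the excess emerges after the 24-subject look, no boundary exists to be crossed.

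**Working it through.** **1. The plan's own boundaries.** The exact lower limit L for x events in n solves P(X ≥ x | n, L) = 0.025 (two-sided 95%).

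| Printed count | Two-sided 95% lower limit | Above 33%? | Smallest count that qualifies | One-sided 95% lower limit of printed count |
|---|---|---|---|---|
| 5/6 | 35.9% | yes | 5/6 | 41.8% |
| 8/12 | 34.9% | yes | 8/12 | 39.1% |
| 10/18 | 30.8% | no | 11/18 (35.7%) | 34.1% |
| 13/24 | 32.8% | no | 14/24 (36.6%) | 35.8% |

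Two printed counts do not meet the stated criterion. All four fit a one-sided 95% bound. Both forms are carried below: the interval form (5, 8, 11, 14) and the printed form (5, 8, 10, 13).

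**2. Enrollment left at the last look.** Inputs: 28 subjects (Section 12.3), 12 months of enrollment (Synopsis), 28-day cycles. Assumption: even accrual. The gap between subjects is 12 × 30.44 / 28 = 13.04 days. The look falls 28 days after subject 24 starts. Subject 25 starts 13.0 days after subject 24, subject 26 after 26.1 days and subject 27 after 39.1 days. So 26 are enrolled and 28 − 26 = 2 are spared.

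**3. Dosing still to come.** Assumption: no early discontinuation. At the look, subject i (i ≤ 24) has been on study 28 + 13.04 × (24 − i) days and has had min(7, floor(days/28) + 1) doses.

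- Subjects 1–13: 13 × 7 = 91 doses.
- Subjects 14–24: 6+6+5+5+4+4+3+3+2+2+2 = 42.
- Subjects 25–26: 2.
- Given: 91 + 42 + 2 = 135. Planned: 28 × 7 = 196. Remaining: 196 − 135 = 61 (31%).

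If accrual takes 18 or 24 months instead, about 3 subjects are spared and 51 or 47 doses remain. Under 12-month accrual, cycle 7 is finished (196 days) by 11 subjects at this look. The other 28 − 11 = 17 could enter re-treatment only afterwards.

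**4. What the looks do capture.** Of the 91 + 42 = 133 doses given to the first 24 subjects, 133 − 24 = 109 belong to cycles 2–7. The event definition is not limited to cycle 1, so events after those doses count if they have occurred by the look.

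**5. Chance of stopping.** Exact binomial recursion over the four looks, with each subject's event taken as known at the first look that includes that subject. At a true rate of 50%, the first look stops with probability P(X ≥ 5 | 6, 0.5) = 7/64 = 10.9%.

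- Interval form at 50%: 10.9 + 11.8 + 8.5 + 6.3 = 37.6%, about 38%.
- Printed form at 50%: 10.9 + 11.8 + 20.9 + 7.6 = 51.3%, about 51%.
- At 33%: 3.8% (interval form), 6.2% (printed form).

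Events that emerge in later cycles would be missed at the earlier looks, so these figures are on the high side.

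**6. One further look at 28.** 14/28 has lower limit 30.6% and 15/28 has 33.9%, so the boundary is 15. Added to the interval form:

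| True rate | Four looks | With 15/28 added |
|---|---|---|
| 33% | 3.8% | 4.6% |
| 50% | 38% | 49% |
| 60% | 73% | 84% |

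**The case against.** The rule is one layer of the safety plan. Appendix 1 and Section 6.4 stop treatment for individual toxicity or on the investigator's judgment. Section 3.3 has a toxicity exclusion for re-treatment. Serious events and events of special interest are reported within one business day. The DSMC sees adverse-event summaries and stopping-rule data, can raise issues of immediate concern, and is not said to stop at 24 subjects. All of this stands, but none of it is triggered by a crossing. Subject-level rules respond to one person's event, not to a finding about the population.

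The exposure figures are also fairly called a ceiling. Section 6.4 ends treatment for confirmed progression, and Section 10.1.4 reports that about 16% of patients in pooled monotherapy studies stopped for an adverse event. Re-treatment is open only to subjects who complete all seven cycles and then progress within a year. The direction holds, but the actual number of later doses will be below 61.

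Three stronger readings are tempting and are not supported:

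- **A reader might infer that later-cycle toxicity is never tested.** Finishing one cycle fixes when a look occurs, not which events count. Step 4 shows substantial later-cycle exposure already inside the last look.
- **A reader might infer that the protocol contradicts itself by ordering dosing to continue after a crossing.** It is silent, and continuation is only an inference from that silence.
- **A reader might infer that six-monthly DSMC meetings would see three of the four looks only after enrollment ends.** That depends on look 2 falling at month 6.06, about two days after an assumed month-6 meeting. If the first subject enrolls at month 0, it falls at month 5.6. Six months is also a minimum frequency, and Section 12.7 does not make a halt wait for a meeting.

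**Conclusion.** The point holds in this form. Section 12.7 gives a population-level toxicity finding one stated consequence, halting enrollment, and applies it last at 24 of 28 subjects. Under even 12-month accrual that spares about 2 subjects (about 3 if accrual takes 18 to 24 months), with up to 61 of 196 initial doses and most re-treatment still ahead. Later-cycle events enter only as far as they have accrued, the counting window is not spelled out, and nothing formal follows the 24-subject look.

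At a true rate of 50%, 62% of trials pass all four looks under the interval form and 49% under the printed counts. Quoting only the 38% stopping chance would understate the rule as printed. The mismatch between the printed counts and the two-sided 95% criterion is a separate inconsistency that must be resolved whichever form was meant.

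The sizes rest on even accrual, no early discontinuation, and each subject's event being known at the first look that includes that subject. The gap in the text rests on none of these.

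**What to change.** - Add one look with all 28 subjects dosed, under the same interval criterion: 15 of 28, lower limit 33.9%. Enrollment is complete by then, so this look has a purpose only together with the referral in the last item.
- State that treatment-related Grade ≥3 events from all cycles and from re-treatment count at every look.
- Report each look to the DSMC when it occurs, not at the next scheduled review.
- Reconcile the printed 10/18 and 13/24 with the two-sided 95% criterion.
- Reconcile Section 12.7 with Sections 5.1.3 and 6.4 by stating that any crossing is referred at once to the DSMC, which decides what applies to subjects on drug or eligible for re-treatment. The clinical action itself is not proposed here.

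The cost is protocol wording and a few short reports from data that HCRN already supplies. In the interval form, the false-alarm chance at a true 33% rate rises from 3.8% to 4.6%, and the chance of stopping at 50% rises from 38% to 49%. Repeating the unadjusted test at every later DSMC review would be a further choice with its own false-alarm cost, and this point does not depend on it.
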